14.1 Investigational Product

3M will label, package, and ship the Cavilon Advanced Skin Protectant product to each research facility participating in the study. Each Cavilon Advanced Skin Protectant pouch will be labeled with the following minimum information:

- Study Number EM-05-012990
- 3M Health Care, [name]
- 3M[™] Cavilon[™] Advanced Skin Protectant
- Lot number PPE-R30-01
- Package content: single-use applicator with ampoule
- Non-sterile Solution. Applicator is sterile if package is intact

3M Confidential

- Use as directed in protocol. See Instructions for Use.
- DANGER! HIGHLY FLAMMABLE!
- Store at room temperature
- Expiration date July 2017

Instructions for Use (IFU) is provided in Appendix B.

14.2 Other Products

Other products supplied by the sponsor will contain a label indicating that these materials are for use in this study. Each commercial product supplied by the sponsor will be in the product's original commercial packaging.

The following materials will be provided:

- 3M[™] Cavilon[™] No-Rinse Skin Cleanser , #3380 (Appendix C)
- ConvaTec Sensi-Care® Protective Barrier (part number 325614) skin protectant paste with zinc oxide (Appendix D)
- Colorplast Brava[™] Adhesive Remover Wipe
- Medline Ultra Soft Dry Disposable Washcloths (UltraSoft10x13)

14.3 Photographic Equipment

3M will provide all photographic supplies necessary for the conduct of this study through vendor, Biomedical Systems. At the conclusion or termination of this study, the Investigator agrees to return all cameras and photographic materials, provided by 3M, in accordance with instructions provided by the study monitor. Biomedical Systems will provide all cameras preset to the same setting for all sites as well as QC photographs. Use of the cameras and downloading photographs to the eDC system will be provided by Biomedical Systems.

15. Cavilon Advanced Skin Protectant and ConvaTec Sensi-Care Protective Barrier Accountability

3M requires Investigators to maintain accountability and adequate inventory security of the Cavilon Advanced Skin Protectant product and comparative product at all times. The Investigator or designee will:

- Upon receipt of Cavilon Advanced Skin Protectant product, check the contents and return the completed Confirmation of Release and Receipt of Clinical Supplies form to the sponsor's study monitor.
- Keep Cavilon Advanced Skin Protectant product in a secure storage area, accessible only to authorized individuals
- Dispense Cavilon Advanced Skin Protectant product only to subjects properly enrolled in the study
- Return all unused Cavilon Advanced Skin Protectant product to 3M at the end of the study, or dispose of as agreed upon

16. Data Collection

16.1 Source Data

Case Report Forms (CRFs) will be provided for each subject. All required data will be recorded on the CRFs. Completed CRFs will be reviewed by the site monitor to ensure completeness and consistency and to ensure adequate quality control and assurance of subject data. Any discrepancies found during CRF review are to be clarified by the Investigator or designee.

The subjects' medical records will be the source data for medical history and current IAD treatment regimen. Data collection forms will also be used. Data collection forms are source documents which must be retained by the Investigator such as the 3M validated Skin Condition Assessment Tool. Information and data recorded on a data collection form must be accurately transcribed to the appropriate CRF. Discrepancies between a medical record, or data collection form, and a CRF are to be resolved by the Investigator or designee.

The Investigator or designee must record all required subject data. An explanation must be documented for any missing data. The Investigator must attest that the data provided represents a complete and accurate record of each subject's participation in the study.

16.2 Computerized Systems

The following systems: eMatrix, SAS version 9.2, Word, and EDC, will be used to create, modify, maintain, archive, retrieve, transmit, analyze, and store data.

16.3 Case Report Forms

3M intends to use electronic data capture (EDC) software for this study. Sites will be trained on the EDC software prior to study enrollment. Each site will be provided with a manual, including instructions on how to complete the electronic CRFs and how to make CRF corrections. Data may be recorded on data collection sheets prior to data entry into the EDC, or may be entered directly into the EDC system. Once the forms are completed, the monitor will review the CRFs to ensure accuracy and completeness. The Investigator must review and sign the CRFs for each subject in a timely fashion following completion. Data for this study will be entered on the CRFs:

CRF	Screening & Enrollment	Days 1-22 or early discharge	Days 23-42 or discharge	End of Study
Inclusion/Exclusion	x			
Subject History	x			
Medications	x	х	х	х
Braden Scale	x			
EQ-5D-5L Questionnaire	x		х	х
Incontinence Care		х	х	х
IAD History & Initial Skin Assessments	x			
3M Skin Assessment		x	х	x
Product Application		x	х	
Healthcare Worker Ease of Use Survey		x	х	x
Incontinence Episodes		x	х	x
Adverse Event		x	Х	x
Protocol Deviation		x	Х	x
Study Exit				х

17. Potential Risks and Benefits

17.1 Study Risks

The potential risks involved in this clinical study are considered to be consistent with those associated with similar skin protectant products used for the management and prevention of IAD. At this time, there are no known risks associated with Cavilon Advanced Skin Protectant.

17.2 Risk Minimization Actions

Additional risks may exist. Measures which have been taken to minimize risks include:

- The selection of Investigators trained in IAD management and prevention
- Specific Investigator and study nurse training on the use of Cavilon Advanced Skin Protectant
- A well-defined clinical protocol, including specific inclusion/exclusion criteria, to enroll appropriate subjects in the study

Risks can be minimized at the clinical site through:

- Compliance with this protocol
- Performing assessments in the appropriate hospital environment
- Adherence to subject inclusion/exclusion criteria
- Close monitoring of the subject's status during follow-up

17.3 Anticipated Benefits

The potential benefit of this product is that it will provide better skin protection of damaged skin against irritants such as feces and/or urine versus currently available skin protection products such as pastes and ointments. In addition, it is able to attach to moist or wet, damaged skin forming an adherent, protective coating that creates an environment for healing. Furthermore, it provides a durable coating that resists removal with routine cleansing practices; therefore fewer applications of barrier film are needed. Unlike current protective paste products, stool does not embed into the film, preventing the need for more frequent and potentially irritating cleansing episodes. The investigational product is expected to be more comfortable for patients to wear and does not transfer to other surfaces such as undergarments, absorbent pads, and bedding. These properties make the product more user friendly for both patients and clinicians.

17.4 Risk to Benefit Rationale

The study product is investigational and is classified as non-significant risk. Based on data collected in previous studies, the risk-to-benefit ratio is within reason for foreseeable risks. However, appropriate observation and follow-up of subjects, will still be required as outlined in the protocol.

18. Safety Reporting

Adverse events will be collected for subjects beginning at Day 1 through the final study visit, or until the subject is discharged from the facility. An adverse event is any symptom, sign, illness, or experience, which develops or worsens during the course of the study, which may or may not be considered investigational product related. The principal measures of safety will be the incidence of adverse events reported during the study.

An anticipated adverse event in this study is a skin reaction to the investigative product itself. Worsening of IAD is expected in this subject population and would therefore not constitute an adverse event (related to the product being tested).

The Adverse Event CRF will be used to capture any safety-related concerns.

18.1Adverse Events

The Investigator is responsible for identifying and reporting adverse events experienced by each subject throughout the study. An adverse event can occur at any time during the conduct of the study, in any phase of the study, or after the study is completed. An adverse event can be identified by the Investigator or reported by the subject.

Note: The Federal Privacy Rule (HIPAA) specifically permits the use and disclosure of protected health information "without written authorization of the individual" when used for public health activities such as reporting adverse events, tracking FDA-related products, enabling recalls, repairs, replacements, lookbacks, or conducting post-market surveillance [45 CFR 164.512]. This use and disclosure is subject to the *minimum necessary* standard, i.e. "the minimum necessary to accomplish the intended use, disclosure, or request" [45 CFR 164.502(b)(1)].

An adverse event is considered to be serious if it is:

- Life threatening of results in death
- Causes in-patient hospitalization
- Unduly prolongs hospitalization
- Persistently or significantly disabling
- A congenital anomaly
- Requires intervention to prevent outcomes above

Severity:

All adverse events will be classified as one of the following severities:

Mild: Subject is aware of signs or symptoms but they are easily tolerated.

Moderate: Signs or symptoms are sufficient to restrict but not prevent subject's daily activity.

Severe: Subject unable to perform daily activity.

Definitions:

- Adverse event (AE) means any undesirable clinical occurrence in a subject whether or not it is considered to be device related.
- Device-related adverse event (i.e. adverse device effect) is an AE considered by the Investigator to have a reasonable likelihood of being associated with the investigational device.
- Serious adverse device effect (SADE) is a device effect that has a serious adverse effect on health or safety causing hospitalization or prolonged hospitalization, or is life threatening or causes death.
- Unanticipated adverse device effect (UADE) is any serious adverse device effect on health
 or safety or any life-threatening problem or death caused by, or associated with a device if that
 effect, problem or death was not previously identified in nature, severity or degree of incidence
 in the investigational plan or application, or any other unanticipated serious problem associated
 with a device that relates to rights, safety and welfare of subjects.

18.2 Adverse Event Recording and Reporting

All adverse events will be recorded on the Adverse Event CRF. The Investigator will record each product-related adverse event on an Adverse Device Effect Record. Event documentation will include the description, severity, seriousness, date of onset and resolution, relationship to the investigational product, action taken, and outcome.

Relatedness:

Definitely related:	Follows a reasonable temporal sequence from investigational product application, and cannot be reasonably explained by known characteristics of the patient's clinical data.
Possibly related:	Follows a reasonable temporal sequence from investigational product application but could have been produced by the patient's clinical state regardless of the investigational product.
Probably not related:	Temporal association is such that the investigational product is not likely to have had any reasonable association with the observed event.
Not related:	No relationship to investigational product is perceived

Not related: No relationship to investigational product is perceived.

The Investigator must promptly report an adverse device effect to the site monitor. If the adverse device effect is also considered by the Investigator to be serious and/or unanticipated, the Investigator must report it to the IRB as soon as possible and within IRB requirements.

A serious adverse event (SAE) involving a non-3M commercialized product is to be reported to the site monitor and the IRB.

If a subject has no adverse device effect during the study, the absence of such must be recorded on the CRF.

19. Statistics

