7.3 Safety Endpoints

Assessment of the safety of Cavilon Advanced Skin Protectant compared to the comparative product will be based upon analyses of the number and percent of subjects with an adverse event (AE) and the nature of each AE. The data will be summarized for each group based on the number and percent of subjects reporting AEs and will be summarized by product group and overall. In addition, AEs will be categorized and then summarized by relation to product and severity/intensity. Incidence of discontinuation will be summarized by reason for discontinuation for each product group.

8. Study Population

The study population will consist of subjects suffering from severe Category 2 Incontinence-Associated Dermatitis where the epidermis has been breached, or the skin is denuded, and who are

in a facility that provides nursing care 24 hours a day. Subjects' incontinence may be urinary and/or fecal, and can be continuous or non-continuous during the 21-day follow-up period. The subjects should not have any pre-existing fungal infections or stage 3, or stage 4 pressure ulcer(s) in the sacrococcygeal and buttock area. Subjects with Stage 1 or Stage 2 pressure ulcers maybe enrolled. (Note, no dressings are allowed for Stage I/II pressure ulcers.) Subjects with ostomies may be enrolled if the anal opening is present and there is evidence of denudement in the perianal or surrounding areas. Also subjects with fecal management systems may be enrolled if there is evidence of denudement in the perianal or surrounding areas. Subjects enrolled must meet the Inclusion/Exclusion criteria set forth in Section 8.1 and 8.2.

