19.2 Sample Size Justification

From a pilot study, the standard deviation of the percent change from baseline was estimated at 70%. A sample size of 51 patients per treatment group has at least 80% power to detect a mean difference of 45% change from baseline. The hypotheses tested will be:

 $H_0: \mu_T = \mu_C = 0$ versus $H_A: \mu_T \neq \mu_C$, where the subscript T = the investigational product and C = Control, the paste product.

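### Adverse-event relatedness is defined only against the investigational product, so the summary by relation to product is not like-for-like between arms, and section 18 is unclear on how IAD worsening is classified.

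*Combined protocol and SAP*

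**What the plan says.** Section 18.2 defines four relatedness grades. The highest reads "Follows a reasonable temporal sequence from investigational product application, and cannot be reasonably explained by known characteristics of the patient's clinical data", and the lowest reads "No relationship to investigational product is perceived". The two between them also refer to the investigational product; the second-highest opens, like the highest, with "Follows a reasonable temporal sequence from investigational product application". The event record is to include "relationship to the investigational product, action taken, and outcome". In 18.1, a device-related adverse event is tied to the investigational device. None of these definitions mentions the comparative paste.

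The term is not generic. In the hypotheses in 19.2, "the subscript T = the investigational product and C = Control, the paste product". Section 19.1.1 describes subjects switching from the comparative product to the investigational one, and section 22 lists the two separately for accountability.

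Section 7.3 plans counts of adverse events by product group and overall, and adds that "AEs will be categorized and then summarized by relation to product and severity/intensity". Section 19.1.2 compares overall incidence between groups in all randomized subjects.

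Section 18 states: "An adverse event is any symptom, sign, illness, or experience, which develops or worsens during the course of the study". It then says: "Worsening of IAD is expected in this subject population and would therefore not constitute an adverse event (related to the product being tested"; the bracket closes there and the sentence ends.

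**The concern.** Comparing safety is part of the primary objective (5.1). For a topical product, the events a reader will look for first are those attributed to the product. A causality scale that names one of the two products gives a related-event count that cannot mean the same thing in both arms: the test arm can accumulate related events, and an arm receiving only paste cannot. The imbalance would come from the form, and its direction is against Cavilon.

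The second problem concerns the condition under treatment. Appendix A scores epidermal loss and skin color, signs that a local reaction to either product could share. The nurse applying the product is not blinded (6.2), and the protocol does not tell sites how to separate a reaction from worsening IAD. How section 18 classifies worsening therefore affects what reaches the adverse-event record, and sites could read it differently.

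**Working it through.** The plan states no figure on this point, so the check is of wording.

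**Step 1. Apply the 18.2 scale to the same event in each arm.** Take a non-serious contact reaction shortly after application.

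| Grade in 18.2 | Subject on Cavilon | Subject who has had only paste |
|---|---|---|
| Definitely related | open | closed: no investigational product was applied |
| Possibly related | open | closed, for the same reason |
| Probably not related | open | unrelated end of the scale |
| Not related | open | the literal answer |

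Both upper grades require a time sequence from application of the investigational product. A subject who has had only paste has no such application.

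**Step 2. Look for another route for the paste.** Section 18.2 sends serious events involving a non-3M commercialized product to the site monitor and the IRB. That is a reporting route for serious events and supplies no causality grade. The anticipated skin reaction in section 18 is named only for the investigative product. No relatedness scale for the paste is given.

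**Step 3. Carry this into the 7.3 summary.** If it is split by arm, related events in an arm receiving only paste are absent by definition. If it is pooled, it describes events related to Cavilon and says nothing about the paste.

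**Step 4. Add crossover.** Under 6.4, paste subjects may move to Cavilon: adults not healed at 21 days with ongoing incontinence, and pediatric subjects not improved within 3 days. A subject randomized to paste can then have a related event, but only after the switch and only attributed to Cavilon. Related events in the paste arm are thus possible, but they are not paste events.

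**Step 5. Read the two section 18 statements together.**

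- *Reading A: IAD worsening is not an adverse event.* This contradicts the definition in the same section and the broad definition in 18.1, and worsening leaves the adverse-event data.
- *Reading B: it is an adverse event but never one related to the product.* The definition is kept, but causality is fixed by rule, although 18.2 has the investigator grade each event.

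The bracket does not settle which is meant. Either reading weakens the safety comparison.

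**Step 6. Identify what is unaffected.** Section 18 makes adverse-event incidence the principal safety measure. All adverse events are recorded (18.2) and overall incidence is compared whatever the causality (19.1.2). The scale does not enter that comparison. Under reading A, events classed as IAD worsening would be missing from it in both arms.

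**The case against.** The best defense is that relatedness is only an additional descriptive summary, that 7.3 does not expressly say it is split by arm, and that sites may in practice read product as the assigned product. The adverse-event CRF instructions, which section 11.1 cites and which are not in the documents, may say so. This limits how far the bias would show. It does not supply a rule, because the protocol text names one product throughout.

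A reader might infer that local skin harm goes uncounted. The documents do not support that. Under 19.1.1, IAD scores are analyzed in both arms at each visit and at the last visit, stinging or burning on application is compared by arm, prevention of IAD in unaffected areas is tested, and fungal infections and pressure ulcers are summarized. Section 7.3 also summarizes discontinuations by reason for each group. What these data lack is severity, seriousness and causality for worsening as a safety event. They are also not complete: front-of-body perineal skin receives product but is not graded for IAD (11.1), and the assessments in section 11 list pain scores but no item for stinging or burning.

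A reader might also infer that IAD worsening is ruled out as an adverse event. That ignores the closing qualifier, which permits reading B. The fair description is ambiguous.

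Following expected disease worsening through the efficacy score is a defensible choice. It argues against making every rise in the Appendix A total an adverse event, since a change of one color band moves the score by one point. It does not resolve the contradiction in section 18.

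**Conclusion.** The point holds in two parts.

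- **Relatedness.** The scale, the event-record item and the device-related definition cover one product, so the summary by relation to product is not like-for-like and, read by arm, is biased against Cavilon. This assumes that sites apply the wording as written.
- **IAD worsening.** Section 18 contradicts itself or decides causality in advance, depending on how its bracket is read.

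It does not follow that safety cannot be compared between arms: overall incidence can be, as planned. Nor can a number be put on the imbalance. A reader might assume a reaction rate, multiply by 51 per arm and set the result against zero, but the documents give no such rate, and a zero would need wholly literal grading at every site. The direction is clear and the size is unknown. The matter is worth correcting because safety is in the primary objective and the change is cheap.

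**What to change.** 1. In 18.1 and 18.2, define relatedness, including the event-record item and the device-related definition, against the study product being applied at the time of the event (Cavilon or Sensi-Care). Both arms, and subjects who cross over, are then graded on one scale.
2. In 7.3, state that the relatedness summary is presented by product group, and show events after crossover under the product then in use.
3. Reconcile the two statements in section 18. Say whether IAD worsening is recorded as an adverse event, and do not settle its relatedness in advance.
4. In the safety section, tabulate by arm the number of subjects whose IAD score worsened from baseline, using scores already collected. State which visits count, because the last visit alone would miss earlier worsening. The table will not cover the ungraded perineal area, and a footnote should say so.

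The cost is slightly more adverse-event grading at sites and one extra table. No visit, procedure or test is added.

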19.1 Statistical Methods

19.1.1 Efficacy Analyses

The primary analysis will be the percent change from baseline to last visit in IAD scores. The IAD score at each time point will be estimated using the assessments at each time point. The percent change from baseline will be calculated at the last visit and compared between treatment groups using an analysis of variance with site, treatment, age group (infants vs adults) and interactions as factors in the model. Lack of significance (P<0.05) for the age group-by-treatment will be used as justification for pooling the age groups. If the interaction is significant, the age groups will be analyzed separately. If appropriate, non-parametric procedures (e.g. ranking the data prior to analysis) will be used.

The primary analysis will be done using an intent-to-treat (ITT) population, using all subjects who have at least one dose of their assigned product. For this analysis, dropouts will be considered censored at the time of dropping out. Because two primary endpoints are being tested, Hocherg's procedure will be used to determine statistical significance to preserve the Type I error rate of α =0.05.

A second analysis will be done using a per protocol (PP) set. This analysis will be done on those subjects who were compliant with therapy and completed all procedures. This dataset will be defined prior to database lock, and all reasons for exclusion will be documented.

Analytical methods will be defined in detail in the approved Statistical Analysis Plan (SAP).

Secondary efficacy endpoints in this study will include:

- Time to resolution of severe Category 2 IAD, defined as re-epithelialization of skin. The time to resolution will be tested using a Cox Proportional Hazards model, with treatment group as a fixed factor in the model, and center as a random factor in the model. Other important prognostic factors (e.g., age, type and intensity of incontinence, use of corticosteroids, diabetes, use of warfarin) will be identified and may be included as covariates in the model. Kaplan-Meier estimates of time to re-epithelialization will also be done.
- Pain scores during incontinence management will be measured on a 0-10 scale, and will be analyzed only for those subjects from the ITT dataset who can report pain. This dataset will exclude those who are paraplegic or cannot respond. Infant pain will be measured with the FLACC tool⁴², and adults with the 0-10 Faces tool, and the data will be combined for statistical analysis. For this dataset, the pain scores will be compared by day using an analysis of variance with center, product, age group (infants vs adults), and interactions as factors in the model. If the age group-by-treatment interaction is significant (P<0.05), the data will be analyzed by age group. This response will be considered significant using a Hochberg's procedure for adjusting the P-values for this and the other secondary response of time to re-epithelialization.

- The proportion of subjects on each treatment group with stinging or burning upon application will be compared using a Cochran-Maentel-Haenzel test, stratifying for center.
- Percent change in IAD scores at each visit.
- Efficacy in subjects who switch from the comparative product to the investigational product after failure on the comparative product. For this analysis, the proportion of subjects with resolution of IAD as defined above will be estimated.
- Prevention of IAD in areas that had no denuded skin and remained free of IAD throughout the intervention. This will be estimated and tested using a Cox Proportional hazard model.
- Prevention of IAD, as measured by IAD scores in subjects whose IAD re-epithelialized and who continued on the investigational product. The proportion of subjects who have no progression of IAD, while still experiencing incontinence, will be estimated.
- Patient Quality of Life (QoL) as measured by the EQ-5D-5L questionnaire will be analyzed by comparing the change from baseline in each of the domains. The changes from baseline will be compared using an analysis of variance with center, product, type of skin (denuded or not), and interactions as factors in the model.
- Nursing time will be summarized for a fecal episode occurring post Dose 1 (after first treatment) for a subset of subjects. The nursing times will be summarized for both product groups.
- Incontinence product use will be recorded during the study, and summarized for both product groups. The purpose of this analysis is to provide estimates of total IAD management cost for both regimens.
- Prevention of complications such as fungal infections and or pressure ulcer development will be summarized.
- Environmental cleanliness of multi-use comparative product packaging. The definition of a "clean" device will be one with a reading of <200. The proportion cleaned will be summarized.

